7.3.3 Serious Adverse Events

A **serious AE (SAE)** is any untoward medical occurrence that at any dose:

- results in death
- is life-threatening (see below)
- requires hospitalization or prolongation of existing hospitalization
- results in persistent or significant disability/incapacity
- is a congenital anomaly/birth defect
- is another important medical event

NOTE: The term 'life-threatening' refers to an event in which the patient was, in the view of the reporting Investigator, at immediate risk of death at the time of the event; it does not refer to an event which may hypothetically have caused death had it been more severe.

Medical judgment should be exercised in deciding whether an AE/ADR is serious in other situations: Important AEs/ADRs that are not immediately life-threatening or do not result in death or hospitalization but may jeopardize the patient or may require intervention to prevent one of the other outcomes listed in the definitions above, should also be considered serious.

In addition, although not classified under the seriousness criteria, all suspected transmissions of an infectious agent should be reported as SAE. A suspected virus transmission means that virus antigen has been detected in the patient. A passive transmission of antibodies alone does not constitute a suspected virus transmission.

7.3.3.1 SAE Reporting

All SAEs, whether or not they are suspected to be related to study treatment, are to be reported immediately to the Octapharma Project Manager by email and to [REDACTED].

In addition, within 24 hours after recognition of the event, an Octapharma Serious Adverse Event Report must be completed and submitted to:

Octapharma's Corporate Drug Safety Unit
OCTAPHARMA Pharmazeutika Produktionsges.m.b.H.
[name]

SAE reporting procedures are outlined in the Site Safety Reporting Manual that will be provided to each site and will be communicated at the site initiation visit.

Waivers from the SAE Reporting Requirement

Waivers from the SAE reporting requirement include surgeries that are elective or were planned before study entry or prolongations of existing hospitalizations for economic or social, but not medical, reasons. Such surgeries or prolongations of hospitalizations should not be considered SAEs. In addition, any AE that meets the criteria of an SAE but begins prior to the start of the first infusion will be waived from the SAE reporting requirements.

7.3.4 Laboratory Tests

The following laboratory tests will be performed during the course of the study to investigate the efficacy, safety, and tolerability of CUTAQUIG (Table 9). At each visit, laboratory tests will be performed before CUTAQUIG infusions at the study site.

The following laboratory parameters will be investigated during the study at the time points specified in the FLOW CHARTS OF ASSESSMENTS.

Table 9: Laboratory Tests and Time Points

Test	Timing	Laboratory
Total serum IgG trough levels	Screening Visit; Stabilization Period Week 0; all subsequent Treatment Period Visits, and Termination Visit	Central
Hematology (complete blood count, WBC differential, hematocrit, hemoglobin)	Screening Visit; Stabilization Period Week 0; Treatment Period Baseline, Week 12, and Week 24; and Termination Visit	Local
Clinical chemistry (sodium, potassium, glucose, ALT, AST, LDH, total bilirubin, blood urea nitrogen or blood urea, creatinine)	Screening Visit; Stabilization Period Week 0; Treatment Period Baseline, Week 12, and Week 24; and Termination Visit	Local

Test	Timing	Laboratory
Urinalysis (pH, glucose, ketones, leukocytes, hemoglobin)	Screening Visit; Stabilization Period Week 0; Treatment Period Baseline, Week 12, and Week 24; and Termination Visit	Local
Urine pregnancy test (females of childbearing potential)	Screening Visit; Stabilization Period Week 0; Treatment Period Baseline, Week 12 and Week 24; and Termination Visit	Local
Virology (HCV-Nucleic Acid Testing [NAT])	Stabilization Period Week 0: CUTAQUIG—naïve patients and SCGAM-03 patients if commercial SCIG product used following completion of SCGAM-03. Treatment Period Baseline: patients currently active and established on CUTAQUIG in SCGAM-03 at the Screening Visit Termination Visit: all patients	Central
Serum retention samples	Stabilization Period Week 0: CUTAQUIG—naïve patients and SCGAM-03 patients if commercial SCIG product used following completion of SCGAM-03. Treatment Period Baseline: patients currently active and established on CUTAQUIG in SCGAM-03 at the Screening Visit Termination Visit: all patients	Central

The methods of determination and normal ranges for each parameter will be provided in the clinical study report.

7.3.5 Serum Retention Samples

Serum retention samples will be collected at Stabilization Period Week 0 for CUTAQUIG-naïve patients or SCGAM-03 patients that have gone on a commercial SCIG product, at Treatment Period Baseline for patients who are enrolled in SCGAM-03 and directly entering SCGAM-06, and at the Termination Visit for all patients (Table 9). These samples will be shipped to a central laboratory for retention and possible future testing of Hepatitis A, B, C, and HIV I/II. Instructions for sample handling will be provided in the Study Laboratory Manual.

7.3.6 Vital Signs

Vital signs will be measured at the time points specified in the FLOW CHARTS OF ASSESSMENTS and include blood pressure, body temperature, pulse, and respiratory rate.

7.3.7 Physical Examination including Height and Weight

Physical examinations will be performed according to each study site's routine procedures by study personnel who are qualified to perform such evaluations. These examinations will be as comprehensive as necessary to detect relevant somatic or neurological diseases. If any findings are abnormal, the Investigator will document the start date and whether or not the abnormal finding is still present at the start of treatment.

Both height and weight will be measured at Screening. In addition, weight will be measured at all visits prior to dosing in order to allow for dose calculations.

7.3.8 Other Relevant Safety Information

7.3.8.1 Post-study related safety reports

Any SAE which occurs up to 4 weeks after the Termination Visit should be reported by the Investigator to the Sponsor in case the Investigator becomes aware of it. Proactive monitoring for post-study SAEs is not required.

If a post-study SAE is identified, the Investigator should complete an SAE form and also record the relationship of the SAE to the IMP in the SAE report.

Any death occurring within 4 weeks after Termination Visit should also be reported, regardless of whether or not it is considered treatment-related.

7.3.8.2 Pregnancies

Every effort will be made to avoid a pregnancy during the use of an IMP. Pregnancies occurring during the study (fetal exposure to the IMP) need to be reported.

In case of a pregnancy during the study, the Investigator should complete the Pregnancy Notification Form and email or fax it to the Sponsor's representative (Section 7.3.3.1).

7.3.8.3 Drug overdose, interaction, or medication error

The following safety relevant information should be reported as AE or as an SAE if the reaction fulfils one of the criteria for seriousness (Section 7.3.3).

a) Drug overdose

An overdose is a deliberate or inadvertent administration of a treatment at a dose higher than specified in the protocol and higher than the known therapeutic dose that is of clinical relevance. The reaction must be clearly identified as an overdose.

b) Drug interaction

A drug interaction is a situation in which a substance or medicinal product affects the activity of an IMP, ie, increases or decreases its effects, or produces an effect that none of the products would exhibit on its own. The reaction must be clearly identified as a drug interaction.

c) Medication error

A medication error involves the inadvertent administration or unintended use of a medicinal product which may be caused by the naming, presentation of pharmaceutical form/packaging, or instructions for use/labelling. The reaction must be clearly identified as a medication error.

7.4 Other Assessments

7.4.1 Drug Concentration Measurements (IgG Trough Levels)

Samples for total IgG trough levels measurements will be taken at the Screening Visit, before any infusion given at the study site (Section 7.1.4), and at the (Early) Termination Visit (Table 9).

7.4.2 Quality of Life Assessment

QoL assessments will be made using the SF-10 from a parent or guardian of patients <14 years of age and the SF-36 Health Survey in patients ≥ 14 years of age. The QoL assessments will take place at the Treatment Period Baseline Visit and at the (Early) Termination Visit.

7.4.3 Subject Questionnaire

The Subject Questionnaire will be completed asking for their opinions related to their participation on the trial. This will be completed by all patients (or with the assistance of a parent/guardian for children, when applicable) at the (Early) Termination Visit.

7.5 Appropriateness of Measurements

Safety will be monitored by standard assessments including monitoring AEs, local infusion site reactions, vital signs, laboratory safety tests, and physical examinations.

Therapeutic efficacy, defined as the prevention of SBI, is a very important clinical aspect of any IgG replacement therapy and best characterizes benefit to the patient.

Determination of the pre-next-dose trough level of IgG is a standard method for determination of the correct dose for the individual patient.

The QoL questionnaires are standardized, validated instruments that have been widely used in clinical studies, including studies with PI patients.

8 DATA HANDLING AND RECORD KEEPING

To ensure that data in the eCRFs are accurate and complete and in accordance with source records, source data verification will be performed in accordance with Octapharma standards. The extent of source data verification will be defined in detail in the monitoring manual.

8.1 Documentation of Data

8.1.1 Source Data and Records

Source data are defined as all information related to clinical findings, observations, or other activities in the study; written down in original records or certified copies of original records; or electronic medical records; allowing reconstruction and evaluation of the clinical study.

The Investigator will maintain adequate source records (eg, case histories or patient files) for each patient enrolled. Source records should be preserved for the maximum period of time required by local regulations.

For each patient enrolled, the Investigator will indicate in the source record(s) that the patient participates in this study.

All data entered in the eCRF must be supported by source data in the patient records, with exceptions listed in Section 8.1.2.

The Investigator will permit study-related monitoring, audit(s), IEC/IRB review(s), and regulatory inspection(s), by providing direct access to the source data/records.

The Investigator may authorize site staff (eg, sub-Investigators, research nurses) to enter study data into the eCRF. This must be documented in the Delegation of Authority Log and signed by the Investigator.

The following data must be verifiable from the source records: patient number, sex, weight, date of birth, written informed consent (and assent, if appropriate), medical history, main inclusion and exclusion criteria, local laboratory test results, PID-relevant concomitant therapies (medication and non-drug therapy), any AE occurring in the course of the study, details of infusions (batch number, number of vials used, date, dose, rate, and infusion site(s)), date and reason for early termination (if applicable). As part of the source records, laboratory data will be reviewed by the Investigator, assessed as to their clinical significance, signed, and dated.

8.1.2 Electronic Case Report Forms

For each patient enrolled, an eCRF will be completed within the EDC system and approved by the Investigator or an authorized sub-Investigator.

Study site staff (eg, research nurse) will be responsible for entering patient data into the validated EDC system. All site personnel will be trained on the EDC system and study specific eCRF before receiving access to the live database for data entry.

The site will be provided with approved eCRF Completion Guidelines which will assist in data entry and data issues/questions. The site will be notified once the database is

active to begin data entry. Additional site training may be provided as refreshers throughout the study, if needed. All persons allowed to enter or change eCRF data must be listed in the Delegation of Authority Log.

If any errors in the eCRFs are found during the data review process, discrepancies will be generated programmatically within the EDC system and manual queries will be generated by either a monitor or Data Management. The programmed edit checks fire automatically once an eCRF page is saved within the system. The outputs of the programmed checks are referred to as discrepancies. Discrepancies are generated by the input of illogical eCRF data with the purpose to clarify the context or insertion of illogical or missing data with the site or designee.

All discrepancies (programmed and manual) will be submitted to the site personnel or monitor for the site within the EDC system. Once the site responds to a discrepancy, Data Management or the monitor will review the new or changed data to ensure an appropriate response and close the discrepancy within the system.

8.1.3 Changes to Electronic Case Report Form Data

Monitors will perform source data verification (SDV) as defined for the study.

Errors occurring in the EDC system can only be corrected by the Investigator(s) or authorized site personnel. An audit trail documents all changes to the data over the entire study period. If data are changed as a result of a query, a comment must be entered stating the reason for the change before closing the query. In addition, any change to a previously saved eCRF page that has not had a query generated will need to have a reason specified for the data change.

Once queries have been resolved by the site staff, the resolutions are assessed by Data Management. If the query response provided confirms the data as correct, the discrepancy will be closed. If the response does not adequately address the question raised, a new query will be issued for further clarification.

Manual checks will be performed, and programs will be run throughout the study until the data are clean (all discrepancies resolved) and the database is ready for lock. Source data verification will be confirmed as complete by the monitor and all eCRFs will be approved by the Investigator before database lock.

8.2 Information to Investigators

An Investigator's Brochure will be provided to the Investigator before the start of the study. This brochure contains all information in the Sponsor's possession necessary for the Investigator to be fully and accurately informed about the safety of the IMP under evaluation and the respective benefit-risk ratio.

The Investigator's Brochure will be updated by the Sponsor at regular intervals and the event that relevant new information concerning the IMP becomes available.

All participating investigators will be informed about relevant study procedures, about the methods for rating relevant study outcomes, and how to enter data into the eCRF in order to reduce discrepancies. At the study initiation visit, the eCRF will be explained to all study site staff entitled to document data in the eCRF.

Investigators will be kept informed of important information related to the safe use of the IMP as the study proceeds.

8.3 Responsibilities

The Principal Investigator is accountable for the conduct of the clinical study at each study site. Responsibilities may be delegated to appropriately qualified persons.

A Delegation of Authority Log will be completed and signed by the Principal Investigator. In accordance with this authority log, study site staff (eg, sub-Investigators, study coordinators, nurses) will be authorized to perform specific tasks relating to study conduct.

At each study site, the Investigator is responsible for maintaining all records to enable the conduct of the study to be fully documented. Essential documents as required by Good Clinical Practice (GCP) guidelines and regulations (eg, copies of the protocol, study approval letters, all original informed consent forms and assent forms (as age appropriate), site copies of all eCRFs, drug dispensing and accountability logs, correspondence pertaining to the study) should be filed accurately and retained by the Investigator for the maximum period of time required by local regulations.

The Investigator is responsible for maintaining a confidential patient identification code list which provides the unique link between named source records and eCRF data for the Sponsor. The Investigator must arrange for the retention of this confidential list for the maximum period of time required by local regulations.

No study document should be destroyed without prior written agreement between the Investigator and the Sponsor. Should the Investigator elect to assign the study documents to another party or move them to another location, the Sponsor must be notified in writing.

8.4 Provision of Additional Information

On request, the Investigator will supply the Sponsor with additional data relating to the study or copies of relevant source records; the Investigator must ensure that patient confidentiality is maintained on any source documents provided to the Sponsor. This is particularly important when source data are illegible or when errors in data transcription are encountered.

In the event of particular issues or governmental queries, it may also be necessary to have access to the complete study records, provided that the patient's confidentiality is protected in accordance with applicable regulations.

8.5 Independent Data Monitoring Committee

The Sponsor will establish an IDMC.

The IDMC will be composed of recognized experts in the field of immunology who are not actively recruiting patients.

During the study, the IDMC will periodically review relevant data and will give advice on the continuation, modification, or termination of the study (Section 6.2.3). A study-

specific Charter will define in detail the composition, responsibilities, and procedures of the IDMC.

Property of Octapharma. Do not copy or distribute without written permission.

9 STATISTICAL METHODS AND SAMPLE SIZE

Statistical analysis will be delegated under an agreement of transfer of responsibilities to an external CRO. All Octapharma procedures and policies must be met by this CRO. Discrepancies or exceptions will be approved by the Sponsor's Manager of Biometrics.

A formal statistical analysis plan describing all details of the analyses to be performed will be prepared by the study statistician and approved by the Sponsor prior to the start of the statistical analysis.

9.1 Determination of Sample Size

Approximately 65 patients who meet eligibility criteria will be enrolled in the study:

- At least 15 patients in Cohort 1
- At least 15 patients in Cohort 2
- At least 35 patients in Cohort 3

The co-primary endpoints will be analyzed descriptively, and no formal sample size calculation was done for the overall number of patients enrolled.

For Cohort 3 we plan for a confirmative analysis to evaluate whether the total IgG trough levels are maintained by an every other week dosing regimen; the following pair of hypotheses will be tested:

$$H_a: T_{eow} > T_w - 1 \quad \text{vs.} \quad H_0: T_{eow} \leq T_w - 1$$

where T_{eow} is the mean total IgG trough on steady-state dosing every other week, T_w is the same for weekly dosing, and a maximum decrease of 1 g/L for the mean total IgG trough level is considered acceptable.

T_w will be determined after completion of the Stabilization Period, T_{eow} at the final study visit.

This one-sided hypothesis will be tested by a paired t-test at the alpha=2.5% level of significance. Assuming 3.0 for the standard deviation common to both members of a pair, and 0.8 as the correlation between members of a pair, this results in a required minimum of 31 evaluable patients to achieve a power of 80%.

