The QoL data will be presented descriptively by visit, along with the change from Baseline Visit.

The Subject Questionnaire data will be presented descriptively.

Name of Sponsor/Company: Octapharma USA, [name]	
Name of Investigational Product: CUTAQUIG	Protocol Identification Code: SCGAM-06
Name of Active Ingredient: Human Normal Immunoglobulin	Date of Final Protocol: 28-Aug-2019

All IgG measurements will be listed and summarized descriptively by time point. Individual courses of IgG trough levels will be presented graphically as Trellis plots.

For Cohort 3 the change in trough total IgG levels from baseline weekly infusions to Week 24 (or Early Termination, if appropriate) of every other week infusions will be evaluated by means of a paired t-test.

FLOW CHARTS OF ASSESSMENTS

Table 1: Screening and Stabilization Periods – Flow Chart of Assessments

ASSESSMENTS	Screening Period	Stabilization Period ⁵		Treatment Period
STABILIZATION PERIOD WEEK NUMBER	Screening ⁴	Week 0	Weeks 1, 2, 3	Baseline
Informed Consent / Assent	X			Patients infuse CUTAQUIG at home. No on-site visits are required. Patients return to the clinic 4 weeks after Stabilization Period Week 0 visit and will enter the Treatment Period and their assigned cohort.
Inclusion/exclusion criteria	X			
Demographics	X			
Medical history	X	X ³		
Body weight	X	X		
Physical examination	X			
Vital signs ¹	X	X		
Urine pregnancy test ^{1, 2}	X			
IgG trough levels	X	X		
Hematology (CBC, WBC differential, hematocrit, hemoglobin) ¹	X	X		
Clinical Chemistry (sodium, potassium, glucose, ALT, AST, LDH, total bilirubin, blood urea nitrogen, creatinine) ¹	X	X		
Urine analysis: pH, glucose, ketones, leukocytes, hemoglobin ¹	X	X		
Serum retention samples ¹			X	
Hepatitis C sample ¹			X	
Receive written Sponsor approval for enrollment including cohort assignment	X			
Infusion using patient's personal, commercially available SCIG product (or CUTAQUIG from Study SCGAM-03, if appropriate) ⁴	X			
Infusion of IMP (on site)			X	
Check for local infusion-site reactions			X	
Patient diary hand-out			X	
Prior / Concomitant medication	X	X		
Adverse events ³			X	

¹ Vital signs will be measured, and all laboratory samples will be collected, before IgG or IMP infusion (if applicable).

² For females of child-bearing potential.

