Patient diary hand-out and check	X	X	X	X	X	X	X	X
Quality-of-Life Questionnaire	X							X
Subject Questionnaire								X
Prior/Concomitant medication	Throughout the study							
Adverse events	Throughout the study							

Required Onsite Visit for all patients.

² Patients entering the study currently active and established on CUTAQUIG in Study SCGAM-03 will have the Baseline Visit performed on the same day as Termination Visit on Study SCGAM-03. Procedures that are performed on the same day as part of Study SCGAM-03 Termination Visit that are also required as part of Study SCGAM-06 Baseline do not need to be repeated at the same visit.

³ Optional Onsite Visit. This visit is not required for patients who are infusing at their maximum rate.

⁴ Vital signs will be measured, and all laboratory samples collected, before IMP infusion (if applicable).

⁵ For females of child-bearing potential.

⁶ Increase flow rates by up to 25 mL/hr/site for patients \geq 40 kg or 10 mL/hr/site for patients $<$ 40 kg every 4 weeks at each site visit until reaching either 1: a maximum flow rate (100 mL/hr/site) or the maximum rate achievable by the pump, or 2) the maximum tolerated flow rate (based on Investigator's decision of patient's tolerance) – whichever is reached first.

⁷ Termination Visit MUST take place prior to the patient receiving any other IgG product.

Table 4: Cohort 3 (Every Other Week Dosing) – Flow Chart of Assessments

ASSESSMENTS		Treatment Period			Termination
TREATMENT PERIOD VISIT WEEK OR TIMING	BL ^{1, 2}	4 ¹	12 ¹	24 ¹	Two weeks after last infusion ⁶
Body weight	X	X	X	X	
Physical examination	X		X	X	X
Vital signs ³	X	X	X	X	X
Urine pregnancy test ^{3, 4}			X	X	X
IgG trough levels ³	X	X	X	X	X
Hematology (CBC, WBC differential, hematocrit, hemoglobin) ³	X		X	X	X
Clinical Chemistry (sodium, potassium, glucose, ALT, AST, LDH, total bilirubin, blood urea nitrogen, creatinine) ³	X		X	X	X
Urine analysis: pH, glucose, ketones, leukocytes, hemoglobin ³	X		X	X	X
Serum retention samples: SCGAM-03 patients not participating in the Stabilization Period ³	X				
Serum retention samples: all patients ³					X
Hepatitis C samples: SCGAM-03 patients not participating in the Stabilization Period ³	X				
Hepatitis C samples: all patients ³					X
Infusion of IMP (on site) ⁵	X	X	X	X	
Check for local infusion-site reactions	X	X	X	X	X
Patient diary hand-out and check	X	X	X	X	X
Quality-of-Life Questionnaire	X				X
Subject Questionnaire					X

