where T_{eow} is the mean total IgG trough on steady-state dosing every other week, T_w is the same for weekly dosing, and a maximum decrease of 1 g/L for the mean total IgG trough level is considered acceptable.

T_w will be determined after completion of the Stabilization Period, T_{eow} at a given subject's final study visit where a valid IgG trough level is collected and reported within a suitable visit window. If a subject terminates from the study prior to the end of study visit (2 weeks following Week 24 infusion), or if a completed subject's end of study IgG trough is not valid or not collected, then the last study visit where a valid IgG trough level was collected will be considered T_{eow} .

This one-sided hypothesis will be tested by a paired t-test at the alpha=2.5% level of significance. Assuming 3.0 for the standard deviation common to both members of a pair, and 0.8 as the correlation between members of a pair, this results in a required minimum of 31 evaluable patients to achieve a power of 80%.

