The use of antibiotics will be summarized descriptively and reported as a detailed list of all such medications, and the number of patients treated with antibiotics, the number of treatment episodes and the number of treatment days will be tabulated. Similarly, systemic antibiotic usage will be presented where antibiotics with the following routes will be excluded: SC, SUBL, OCUL, OTIC, RECT, TOP, BUC, NASAL, TDERM, TOP OD, TOP OS, or TOP OU.

The QoL SF-10 and SF-36 data will be presented descriptively by summarizing derived component scores from PRO CoRE 2.1 Smart Measurement® System software. Observed and change from baseline (defined as the Treatment Period Baseline Visit) data will be summarized by visit for the following derived component scores:

SF-10- Physical Summary Score and Psychosocial Summary Score;

SF-36- Physical Functioning 0-100 and Norm-based Score, Role Physical 0-100 and Norm-based Score, Bodily Pain 0-100 and Norm-based Score, General Health 0-100 and Norm-based Score, Vitality 0-100 and Norm-based Score, Social Functioning 0-100 and Norm-based Score, Role Emotional 0-100 and Norm-based Score, Mental Heath 0-100 and Norm-based Score, Physical Component Score, and Mental Component Score.

The derived scores and the responses from the SF-10 and SF-36 survey questions will be presented in the listings.

Total serum IgG trough levels will be summarized for observed and change from baseline during the Treatment Period for Cohort 1, 2, and 3.

For Cohort 3, the change in total IgG trough levels when switching from weekly to every other week infusions will be tested confirmatory by means of a one-sided, paired t-test at the $\alpha=0.025$ level of significance. The following pair of hypotheses will be tested:

$$H_a: T_{eow} > T_w - 1 \quad \text{vs.} \quad H_0: T_{eow} \leq T_w - 1$$

where T_{eow} is the mean total IgG trough on steady-state dosing every other week, T_w is the same for weekly dosing, and a maximum decrease of 1 g/L for the mean total IgG trough level is considered acceptable.

T_w will be determined after completion of the Stabilization Period, T_{eow} at a given subject's final study visit where an IgG trough level is collected and reported within a suitable visit window. If a subject terminates from the study prior to the end of study visit (2 weeks following Week 24 infusion), then the last study visit where a valid IgG trough level was collected will be considered T_{eow} .

10. Safety and Tolerability Analyses

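### The only confirmatory test uses one late every-other-week trough per patient; averaging the Week 24 and Termination troughs already scheduled would add a little power at no sampling cost

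*Protocol*

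**What the plan says.** Protocol 9.1 and 9.2.2 test, one-sided at 2.5%, whether the mean trough under every-other-week dosing has fallen by less than 1 g/L. T_eow "is the mean total IgG trough on steady-state dosing every other week", determined "at the final study visit". With SD 3.0 and a correlation of 0.8 between members of a pair, Protocol 9.1 states that "this results in a required minimum of 31 evaluable patients to achieve a power of 80" per cent. At least 35 patients are planned for Cohort 3.

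The five places that define the endpoint are close but not identical:

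- **Protocol 9.1 and 9.2.2:** the final study visit.
- **SAP 5:** the "final study visit where a valid IgG trough level is collected and reported within a suitable visit window". The end-of-study visit is placed two weeks after the Week 24 infusion. The last valid trough is used for early terminators, and also for completers whose end-of-study trough is invalid or missing.
- **SAP 9:** the "final study visit where an IgG trough level is collected and reported within a suitable visit window". The fallback covers early terminators only.
- **Protocol synopsis:** the change "from baseline weekly infusions to Week 24 (or Early Termination, if appropriate) of every other week infusions".

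Protocol Table 4 schedules an IgG trough in Cohort 3 at Baseline, Weeks 4, 12 and 24, and at Termination ("Two weeks after last infusion"). Table 9 confirms central-laboratory IgG at "all subsequent Treatment Period Visits, and Termination Visit". Neither document plans to combine the two late values.

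**The concern.** The hypothesis concerns a steady-state level. The schedule yields two late measurements of that level two weeks apart, and only one enters the test. The other is collected and assayed but does nothing for the single confirmatory conclusion. Averaging two measurements of one quantity removes part of the within-patient noise, so the same patients would give a narrower interval for the change.

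The definition itself also needs tidying. A reader of the synopsis would take Week 24, while a reader of the other four places would take Termination in a completer. A completer without a usable Termination trough has a value under SAP 5 but no stated rule under SAP 9. A single definition would settle both matters.

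**Working it through.** **Inputs from Protocol 9.1 (repeated in SAP 5).** Margin 1 g/L, one-sided alpha 0.025, SD 3.0 for each trough, correlation 0.8 between the weekly and the every-other-week trough, paired t-test. True change is taken as zero; neither document says so, but the stated number requires it.

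**Step 1: reproduce the plan's figure.**
Var(difference) = 2 × 9 × (1 − 0.8) = 3.6, so SD = 1.897.
Power from the noncentral t with n − 1 degrees of freedom and noncentrality 1 / (1.897/√n):

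- n=30: 79.7%
- n=31: 81.0%
- n=35: 85.7%

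The smallest n reaching 80% is 31, as stated.

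**Step 2: are both late draws near steady state?** Protocol 1.1 gives a half-life of about 30 to 35 days. The approach to the new steady state after d days is 1 − 2^(−d/half-life).

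- Week 24 (168 days): 96.4% (35 days) to 97.9% (30 days)
- Termination (182 days): 97.3% to 98.5%

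The two draws estimate practically the same level.

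**Step 3: variance with the average.** Let r be the correlation between the two late troughs. It is not in the documents. Give each late trough SD 3.0 and correlation 0.8 with baseline. Then
Var(difference) = 9 × [(1 + r)/2 + 1 − 2 × 0.8].

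| r | Variance | Power, n=31 | Power, n=35 |
|---|---|---|---|
| single trough | 3.600 | 81.0% | 85.7% |
| 0.98 | 3.510 | 82.0% | 86.6% |
| 0.95 | 3.375 | 83.5% | 87.9% |
| 0.90 | 3.150 | 85.9% | 89.9% |
| 0.80 | 2.700 | 90.6% | 93.8% |

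**Step 4: which r is realistic?** Over 14 days, 2^(−14/30) to 2^(−14/35), that is 72% to 76%, of the IgG present at Week 24 remains. The plan's 0.8 describes two different regimens about 26 weeks apart. Two draws 14 days apart on one regimen should correlate more strongly. I therefore use 0.90 to 0.98 and treat 0.80 as an optimistic bound.

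**Step 5: how fragile is the gain?** If Week 24 correlates c with baseline and Termination 0.8, the variance is 9 × [1 + (1 + r)/2 − 0.8 − c]. It equals 3.6, so nothing is gained, when c = 0.8 − (1 − r)/2:

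- r = 0.90: c = 0.75
- r = 0.95: c = 0.775

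Below that value the average does worse than Termination alone. At r = 0.95 and c = 0.75, power at n=31 is 78.7%.

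**Step 6: patients with only one qualifying trough.** If a share q has one, the average variance is q × 3.6 + (1 − q) × the Step 3 value. With q = 0.2 and n=31, power is 84.9% at r = 0.90 and 83.0% at r = 0.95. Simulating this mixed rule at the margin with n=31 (200,000 trials; q of 0, 0.2 and 0.5; r of 0.80 and 0.95) gave one-sided type I error of 0.0246 to 0.0255 against the nominal 0.025.

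**The case against.** The plan meets its stated power with one trough, so using one is a legitimate choice. That stands, and it is why this is offered as an improvement. A reader might go further in four directions that the documents do not support.

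- **That the sample size is wrong.** It is not; 31 reproduces exactly.
- **That the wording of the hypothesis requires averaging within a patient.** The word *mean* reads naturally as the mean over patients, and the weekly comparator is also one draw.
- **That the texts are in broad conflict over the visit.** Four of the five places agree on the final study visit, and SAP 5 pins it to two weeks after the Week 24 infusion. Only the synopsis names Week 24. SAP 9's missing clause for completers is a gap, not a rival definition. SAP 5's *valid* and both SAP sections' *suitable visit window* are undefined, but that is missing detail, not a contradiction.
- **That the Week 24 draw may be a week off a true trough, because Table 7 allows that visit ±1 week.** Table 7 says its windows refer back to the first visit of the period, so this is drift from Baseline. The dosing interval is fixed separately at every other week ±2 days, and Termination at two weeks ±2 days. A draw that respects those rules is already a 12-to-16-day trough.

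The strongest remaining objection is timing. The SAP is version 3.0, dated February 2022, and the last patient visit was planned for the first quarter of 2021. Redefining the only confirmatory endpoint of an open-label study after results could be known would invite more criticism than a few points of power are worth. That objection stands and limits the fix.

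**Conclusion.** The point holds as a low-cost improvement. With both late troughs correlating 0.8 with baseline and 0.90 to 0.98 with each other, averaging adds about 1 to 5 percentage points: from 81.0% to 82.0-85.9% at n=31, and from 85.7% to 86.6-89.9% at n=35.

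A reader might infer a gain of nearly 10 points from the 90.6% at n=31. That needs a correlation of 0.80 between draws two weeks apart, which is an upper bound and not an expectation. The gain is also not assured: at a late-trough correlation of 0.95 it is nil if Week 24 correlates 0.775 with baseline. Both correlations are assumptions, and all these power figures take the true change as zero. Aligning the synopsis and SAP 9 with the other texts is worthwhile whether or not averaging is adopted.

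**What to change.** **If the data have not been analysed.** Put one definition in the synopsis, Protocol 9.1 and 9.2.2, and SAP 5 and 9:

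- T_eow is the mean of the qualifying Week 24 and Termination total IgG troughs.
- A trough qualifies if drawn before infusion and within the protocol's existing interval of 14 ± 2 days since the previous CUTAQUIG infusion.
- If only one qualifies, T_eow is that value.
- If neither qualifies, T_eow is the last earlier qualifying every-other-week trough, following SAP 5's fallback. It is never the Baseline value, which reflects weekly dosing.

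**If analysis has begun.** Keep SAP 5's single trough as primary, align the synopsis and SAP 9 to it (including the fallback for completers), and report the average as a labelled sensitivity analysis. This adds no power to the confirmatory test.

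**Cost.** No extra samples, visits or patients. The first option changes the definition of the only confirmatory endpoint in an open-label study, so it must be fixed and documented before analysis. The timing rule may leave some patients with one trough or with the fallback, which reduces the gain as shown in Step 6.
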